### **3.9 Data Management and Dissemination**

All patient-identifiable data are saved by the assessment team on password-protected fillable PDFs on a secure password-protected and HIPAA-compliant website. On these PDFs, patients and providers are assigned identification numbers. Local trainers who entered the study as Generation 1 providers retain their original provider identification number. Local trainers who enter the study solely to be trainers are assigned an identification number. These identification numbers are then used to link anonymized data that is collected via password-protected Qualtrics. When collecting assessments, assessors call participants and enter the data into Qualtrics. Participants also have the option of entering their data directly into a participant-facing version of the surveys via a HIPAA-compliant version of Qualtrics. Participant-identifiable data is not shared with outside entities during or after the trial. A data management team supervised by the PI (AGH), biostatistician (LD), and postdoctoral scholar (LDS) is responsible for downloading, collating, and analyzing the data.

A Data Safety Monitoring Board has been formed to help prevent and manage adverse events. The board includes members with expertise in SMI, psychosocial treatments, and randomized controlled trials. Members are independent from the PI and competing interests. A report was made to the board bi-annually for the first year of the research of the Implementation Phase (Phase 1). Since then, it has shifted to annual reports. However, if safety issues arise, it will be changed to monthly meetings. Yearly reports are submitted to the Committee for the Protection of Human Subjects at UC Berkeley and National Institute of Mental Health (NIMH). Triyearly reports on recruitment are also submitted to the NIMH.

Organizations not directly involved in the trial (e.g., NIMH, Data Safety Monitoring Board, Institutional Review Board) have the right to audit and, if such a situation arises, will determine the frequency and procedures for auditing. The project management team regularly audits the monthly enrollment as well as the completeness and quality of the data.

Outcomes specifically of interest to our partners are presented to CMHC leadership as part of the widely-used implementation strategy, audit and feedback (83). However, these interim analyses are used only for facilitation purposes and do not address the aims specified herein or by Sarfan et al (2023). Also, they do not influence research procedures in any way (e.g., to inform when to terminate the trial).

Results from the trial, as well as analysis code, will be shared via peer-reviewed publications, professional conference presentations, and meetings and newsletters to CMHCs, as relevant. Other than the authors and compliance with data-sharing agreements stipulated by the National Institutes of Health, no other entities have contractual agreements to access the final dataset. Deidentified data are submitted to the National Institute of Mental Health Data Archive twice per year, per the NIMH requirements.

### **3.10 Roles and Responsibilities**

This trial is supervised by the PI (AGH), who manages the facilitation team, assessment team, and the

data management team. The PI meets with members of each team regularly and as needed in addition to daily email communication. Within each team, there is at least one trained lead (ERA, KF, JMS, LD, LDS) who supervises the day-to-day activities of other team members. There is no coordinating center, trial steering committee, or Stakeholder and Public Involvement Group. The responsibilities of each team are detailed elsewhere in this protocol. In summary, the facilitators execute the implementation of TranS-C via numerous activities, including training and supervising local trainers. The assessment team is responsible for the informed consent process and conducting participant (i.e., provider and patient) evaluations. CMHC leadership and enrolled local trainers and providers work with the facilitation team to recruit additional trainers, providers, and/or patients. Generation 2 providers help to identify potentially eligible patients, who are then connected with the assessment team for formal eligibility evaluation.

### **3.11 Changes to Preregistration**

Originally, all three phases of the trial were preregistered on clinicaltrials.gov on November 6, 2019 (identifier: NCT04154631). However, after much consideration, we decided to separate the three phases (i.e., Implementation, Train-The-Trainer, and Sustainment), in order to thoroughly investigate each phase, thereby maximizing research and partners' resources, and contributing as much as possible to the field. Thus, on April 10, 2023, we created a separate clinicaltrials.gov registration page for the TTT Phase (identifier: NCT05805657). This new page contains the information about the TTT Phase from the original preregistration but more thoroughly articulates the aims, hypotheses, measures, and procedures for this phase. After preregistration of the TTT Phase, we made one additional change. Specifically, given that change from pre-treatment to mid-treatment is not a primary outcome for any measure in the present study, we moved change from pre-treatment to mid-treatment on the Acceptability of Intervention Measure and the PROMIS-Sleep Disturbance measure from the primary outcome section to the secondary outcome section on clinicaltrials.gov.

## **4 PLANNED ANALYSES**

### **4.1 Preliminary Analyses and Missing Data**

All analyses below pertain to the TTT Phase and are limited to Generation 2 providers and Generation 2 patients, except Exploratory Aim 1. For the primary analyses, which use multilevel modeling (MLM) and structural equation modeling, analyses will use all available data (intent-to-treat) (84). Models will be estimated with maximum likelihood estimation, and missing data will be assumed to be missing at random (85). For exploratory analyses using linear regression, approaches to missing data will be based on the number of missing cases (e.g., listwise deletion versus multiple imputation) (86). If dropout is related to other variables, they will be included as predictors. Baseline between-group differences in demographic variables will be examined. These tests will not be used to select covariates in the primary intention-to-treat analysis (87–90). Instead, covariates will be carefully selected at the conclusion of the trial—given the variations due to COVID-19 and the CMHC context (see Discussion)—and the potential influences of baseline differences will be evaluated as moderators (approach to moderation described below). Analyses comparing TranS-C to UC-DT will evaluate change in outcomes from pre-treatment to post-treatment. Analyses comparing Adapted to Standard TranS-C will evaluate change in Generation 2 outcomes from pre-treatment to post-treatment and pre-treatment to 6FU (see Method and Discussion for more details).

Distributions will be evaluated to detect outliers, and we will ensure that the assumptions of planned analyses are met. Covariates will include the patient variables for which we stratified (i.e., age and presence of psychosis or substance use). For all statistical models, counties will be adjusted for as a factor

variable rather than a level of analysis due to the relatively small number of clusters. The average intraclass correlation on provider and patient level outcomes will be reported.

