By the end of the TTT Phase, we project based on current recruitment numbers that we will recruit 130 patients and 60 providers. Using these sample sizes in a cluster randomized trial design, minimum detectable effect sizes were calculated for Aims 1 and 2 using Stata (77) and Aim 3 using Schoemann et al.'s (2017) application. For Aim 1, small to moderate correlations between TranS-C (vs. UC-DT) and sleep outcomes ( $rs = .37\text{-.39}$ ) and intraclass correlation (ICC) of 0.30 were estimated using data from a prior trial (35). The coefficient of variation of cluster size was estimated as 0.72, based on the anticipated ratio of standard deviation of cluster size to mean cluster size for CMHC patients (78). A two-sided alpha of 0.05 was used. Together, the minimum detectable effect size with a sample of 130 patients and 9 clusters was estimated at a large effect size of  $d = 0.94$ . We expect this effect size will be feasible to detect, given that a prior study with a similar aim and same primary outcome produced a similarly large effect size ( $d = 0.96$ ) (35). For Aim 2, prior studies have reported high sensitivity to change and test-retest reliability between measures of fit ( $rs = .83\text{-.85}$ ) (67). Based on the ICC estimated from similar prior provider-level studies (38,79), the ICC was assumed to be 0.20. The coefficient of variation of cluster size was estimated as 0.75, based on the anticipated ratio of standard deviation of cluster size to mean cluster size for providers (78). A two-sided alpha of 0.05 was used. Together, the minimum detectable effect size with a sample of 60 providers and 9 clusters was estimated at a medium to large effect size of  $d = 0.70$ . Although few prior studies are available, one similar trial found a medium effect size ( $d = .53$ ) (80). Because these estimates suggest we might be slightly underpowered for Aim 2, effect sizes will be considered in addition to p-values. For Aim 3, a Monte Carlo power analysis through Schoemann et al.'s

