#### **4.4 Aim 2: Adapted TranS-C versus Standard TranS-C on Fit to CMHC Context**

MLM will be used to account for multiple observations nested within Generation 2 providers. TranS-C treatment condition (Adapted versus Standard TranS-C) will be evaluated as a predictor of fit, operationalized as Generation 2 provider ratings of acceptability, feasibility, and appropriateness. The level 1 equation will include dummy-coded time indicators as the predictor (0 = post-training, 1 = post-treatment). The level 2 equation will include dummy-coded treatment condition (0 = Standard TranS-C, 1 = Adapted TranS-C) and treatment by time interaction terms as predictors, adjusting for county. The treatment effects of interest will be significant treatment by time interactions at the 5% level on the primary outcome of acceptability and the secondary outcomes of feasibility and appropriateness, all modeled as continuous variables. Significant treatment by time interactions indicate that change in perceptions of fit is significantly different comparing Adapted to Standard TranS-C. Significant interactions will be interpreted using planned contrasts (i.e., treatment effects on change from pre-treatment to post-treatment) and graphs.

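### Section 4.1 names maximum likelihood and no small-sample reference distribution; read as full ML with a normal reference, the 5% tests run at about 5.9% in Aim 2 and 5.4% in Aim 1

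*Combined protocol and SAP*

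**What the plan says.** Section 4.1 sets one estimator for the multilevel and structural equation models: "Models will be estimated with maximum likelihood estimation, and missing data will be assumed to be missing at random". The term is unqualified. Restricted maximum likelihood, Satterthwaite, Kenward-Roger, and a z or t reference are not mentioned anywhere.

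Section 4.1 also makes county a factor "variable rather than a level of analysis due to the relatively small number of clusters". The only grouping level left is therefore the patient in Aim 1 (4.3) and the provider in Aim 2: "MLM will be used to account for multiple observations nested within Generation 2 providers". Each has two occasions: pre- and post-treatment for patients, post-training and post-treatment for providers.

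The Aim 2 test in 4.4 looks for "significant treatment by time interactions at the 5% level on the primary outcome of acceptability". Section 4.3 applies the same criterion to sleep disturbance. On size, section 3.8 projects that "we will recruit 130 patients and 60 providers".

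**The concern.** Maximum likelihood estimates a variance by dividing by the number of units and makes no allowance for the fixed effects already estimated. If the resulting ratio is then compared with a normal quantile, uncertainty in that variance is also ignored. Both steps push the same way: intervals come out too narrow and the test rejects too often.

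With hundreds of units this would not matter. Here the primary provider outcome rests on one change score from each of about 60 providers. Section 3.8 concedes that Aim 2 may be slightly underpowered, so a borderline p-value for acceptability is plausible, and there a slightly lenient test could change the wording of the conclusion. Section 3.8 also says effect sizes will be weighed alongside p-values for Aims 2 and 3, so the Aim 2 intervals should have their stated coverage.

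**Working it through.** **Inputs.** From 3.8: 60 providers, 130 patients, 9 clusters, coefficient of variation of cluster size 0.75 (Aim 2), r = .83 to .85 for the fit measures, "the ICC was assumed to be 0.20", and "A two-sided alpha of 0.05 was used". From 4.3 and 4.4: two occasions and a treatment-by-time test. Assumed, because the documents do not say: full maximum likelihood, a normal reference, and 80% power for the detectable effect.

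**The plan's own figure (Aim 2, d = 0.70).**
- Design effect = 1 + [(0.75² + 1) × 60/9 − 1] × 0.20 = 2.883.
- Standard error at r = .83 = √[4 × 2.883 × (1 − 0.83²)/60] = 0.2445.
- Detectable effect = (1.960 + 0.842) × 0.2445 = 0.685.

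This is close to the stated 0.70; r = .84 gives 0.666 and r = .85 gives 0.647. With t on 58 degrees of freedom it becomes (2.002 + 0.848) × 0.2445 = 0.697 at r = .83, so the planning figure hardly depends on the choice of reference.

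**Size of the error, complete data.** With two occasions and a random intercept, the treatment-by-time estimate is the difference between arms in mean change. A county main effect cancels out of each change score. Maximum likelihood divides the residual sum of squares by n, restricted maximum likelihood by n − 2. Hence:

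- ratio of standard errors = √[(n − 2)/n]
- true level with ML and z = P(|t on n − 2 df| > 1.960 × √[(n − 2)/n])

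| n | SE ratio | ML, z | REML, z | ML, t | REML, t |
|---|---|---|---|---|---|
| 60 (Aim 2) | √(58/60) = 0.983 | 5.9% | 5.5% | 5.4% | 5.0% |
| 130 (Aim 1) | √(128/130) = 0.992 | 5.4% | 5.2% | 5.2% | 5.0% |

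The REML, z column shows that restricted maximum likelihood alone does not restore 5%. The t reference is needed as well.

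**Interval width.** The REML interval with t, relative to the ML interval with z, is 2.002/(1.960 × 0.983) = 1.039 in Aim 2 and 1.979/(1.960 × 0.992) = 1.017 in Aim 1.

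**Smaller samples.** The same formula gives 6.1% at n = 48, 6.5% at n = 36 and 7.4% at n = 24. The documents give no sizes for the dose-defined subsets in 4.6, so these only illustrate how the error grows.

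**Missing second ratings (simulation).** The setting was 60 providers in nine unequal counties, county as a fixed factor, no between-county variation in change, and about 6,000 runs per scenario. With 20-40% of second ratings missing (assumed range), the ML standard error was 2-3% below the REML one. ML with z rejected in 5.9-6.6% of runs, REML with t in 4.7-5.1%. For Aim 1, 3,000 runs gave 5.8% (complete data) and 5.0% (20% missing) with ML and z. Monte Carlo error is about 1.96 × √(0.054 × 0.946/3000) = ±0.8 points, so these runs cannot resolve a 0.4-point excess, and the Aim 1 figure rests on the closed form.

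**The case against.** The strongest reply has three parts.

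- **The defect is partly read from silence.** Section 4.1 does not say full maximum likelihood and does not rule out a small-sample correction, and the sentence appears in a passage on missing data. This stands. The figures hold only if the unqualified term means full maximum likelihood with a normal reference. If something else is intended, the same added sentence settles it.
- **The usual reason for a small-sample correction is absent.** A reader might infer that nine counties make the problem severe. With county as a fixed factor, no variance component is estimated from nine clusters. This also stands, but the residual variance still rests on 60 or 130 change scores, so a small bias remains.
- **The effect is small, and the plan already limits its consequences.** Section 3.8 reads effect sizes alongside p-values in Aim 2. True, though those effect sizes will be judged with intervals from the same standard errors.

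A reader might also infer much larger inflation for providers once county-by-time terms enter the model. The documents do not support that. Section 4.4 adjusts for county only as a factor. Condition is assigned by county (Abstract, Methods; note to Table 2), so a full set of county-by-time terms would absorb condition by time. In a design matrix for 60 providers in nine counties, the 19 columns have rank 18. The tested coefficient would not be estimable, so no error rate can be given for it.

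**Conclusion.** The point holds as a minor one. On the stated reading, the Aim 2 standard error is about 1.7% too small and the level about 5.9%, or about 5.9-6.6% under the assumed missingness. For Aim 1 the figures are 0.8% and about 5.4%. The error is somewhat larger in small subsets. This does not invalidate the primary tests.

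Nor should a reader infer that correcting it brings Aim 2 to 5% in general. These figures assume no between-county variation in change. Condition is assigned by county, and a county main effect does not absorb county differences in change over time. The documents give no intraclass correlation for change; the value of 0.20 in 3.8 is not identified as one. If 5%, 10% or 20% of the change-score variance lay between counties (assumed range), simulated levels would be about 11%, 16% and 25% with ML and z, and still about 10%, 14% and 23% with REML and t on 58 degrees of freedom. That issue is separate and needs its own remedy.

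**What to change.** In 4.1, state that the multilevel models in 4.3, 4.4 and 4.7-4.9 are fitted by restricted maximum likelihood, with tests and intervals based on Satterthwaite or Kenward-Roger degrees of freedom. Both parts are needed. Keep full maximum likelihood for the structural equation models in 4.3 and 4.5. State also that this does not deal with between-county variation in change in Aim 2.

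The cost is one sentence and a software option. The observed data used and the missing-at-random assumption do not change. Intervals widen by about 2% in Aim 1 and 4% in Aim 2, and the Aim 2 detectable effect rises by about 0.01 (0.685 to 0.697 at r = .83 and an assumed 80% power).

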### Methods:

TTT will be implemented in nine CMHCs in California, United States (N = 60 providers; N = 130 patients) via facilitation. CMHCs are cluster-randomized by county to Adapted TranS-C or Standard TranS-C. Within each CMHC, patients are randomized to immediate TranS-C or usual care followed by delayed treatment with TranS-C (UC-DT). Aim 1 will assess the effectiveness of TranS-C (combined Adapted and Standard), compared to UC-DT, on improvements in sleep and circadian problems, functional impairment, and psychiatric symptoms for Generation 2 patients. Aim 2 will evaluate whether Adapted TranS-C is superior to Standard TranS-C with respect to Generation 2 providers' perceptions of fit. Aim 3 will evaluate whether Generation 2 providers' perceived fit mediates the relation between TranS-C treatment condition and patient outcomes. Exploratory analyses will: (1) evaluate whether the effectiveness of TranS-C for patient outcomes is moderated by generation, (2) compare Adapted and Standard TranS-C on patient perceptions of credibility/improvement and PhenX Toolkit outcomes (e.g., substance use, suicidality); and (3) evaluate other possible moderators.

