**Table 2. SPIRIT Depiction of Timing and Measures Collected for Train-the-Trainer Phase**

[figure not shown]
	Screening	Post-Training	Pre-Treatment	Mid-Treatment	Weekly During Treatment	Post-Treatment †	6-Months Post-Treatment
Generation 2 Patient							
Sociodemographics			x			x	x
Eligibility Items	x						
PROMIS-SD P	x		x	x		x	x
PROMIS-SRI			x			x	x
DSM-5 Cross-Cutting			x			x	x
SDS			x			x	x
Sleep Health Composite			x			x	x
PHENX Toolkit			x			x	x
CEQ						x	
Generation 2 Provider							
Sociodemographics		x					
Occupation		x					
Acceptability P		x				x	
Appropriateness		x				x	
Feasibility		x				x	
Weekly Session Log					x		

*Note.* Allocation to Adapted or Standard TranS-C occurs at the county level and prior to enrollment of any participants in that county (i.e., patients or providers). Enrollment of patients and allocation to immediate TranS-C or delayed TranS-C (UC-DT) occur after the screening and before the pre-treatment assessment. Enrollment of providers occurs after the training; note: providers may hold a dual role as a local trainer. †Post-treatment assessments for immediate TranS-C and delayed TranS-C (UC-DT) were identical except that the CEQ was not delivered at the UC-DT post-treatment assessment. P = Primary Outcome. PROMIS-SD = PROMIS-Sleep Disturbance; note: PROMIS-SD is only assessed during the pre-treatment assessment if done more than one month after the screening to minimize burden for patients. PROMIS-SRI = PROMIS-Sleep Related Impairment. SDS = Sheehan Disability Scale. CEQ = Credibility/Expectancy Questionnaire.

[figure not shown]

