## 2 AIMS

This study aims to evaluate the implementation and effectiveness outcomes of TranS-C in the CMHCs of counties across California in the United States. As explained above, the present protocol describes Phase 2, the Train-the-Trainer Phase, of a three-part hybrid type 2 effectiveness-implementation study. The Train-the-Trainer Phase builds upon the infrastructure of the Implementation Phase (42). Specifically, during the Implementation Phase, sites are cluster-randomized by county to Adapted TranS-C or Standard TranS-C with 1:1 allocation. External expert trainers train an initial cohort of providers (i.e., Generation 1 providers) in TranS-C via facilitation. Then, within each county, patients are randomized to receive

immediate TranS-C or UC-DT from Generation 1 providers.

In the Train-the-Trainer Phase, expert trainers offer additional training for Generation 1 providers to become “local trainers” in TranS-C. Then, these local trainers train the next cohort of providers (i.e., Generation 2 providers) within their organization in TranS-C (see Figure 1). Then, within each county, patients are randomized to receive immediate TranS-C or UC-DT from Generation 2 providers. Patients treated by Generation 2 providers are referred to as “Generation 2 patients.” Sites retain their original randomization assignment to Adapted or Standard TranS-C. See below for more details on the TTT procedures.

Aims and hypotheses for the Train-the-Trainer Phase mirror the Implementation Phase (42). Parallel analyses to the Implementation Phase will allow us to test the extent to which implementation and effectiveness outcomes are maintained with TTT.

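### County is a fixed factor in every model although Adapted versus Standard is randomised by county: the Exploratory Aim 2 regression then has no estimable condition effect, and the Aim 2 interaction test ignores county differences in change

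*Combined protocol and SAP*

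**What the plan says.** **Allocation.** The abstract says "CMHCs are cluster-randomized by county to Adapted TranS-C or Standard TranS-C". The note to Table 2 adds: "Allocation to Adapted or Standard TranS-C occurs at the county level and prior to enrollment of any participants in that county". Section 2 describes 1:1 allocation of sites by county in the first phase, and sites keep that assignment in this phase. Section 3.3.1 lists nine counties.

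**County in the models.** Section 4.1: "For all statistical models, counties will be adjusted for as a factor". The reason given there is the small number of clusters, and county is expressly not made a level of the models. Sections 4.3, 4.4, 4.7 and 4.9 repeat the adjustment for county. The linear-regression sentence in 4.8 does not, and 4.5 (Aim 3) does not mention county.

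**Adapted versus Standard analyses.**
- Section 4.4 (Aim 2) nests observations within providers, with condition, time, their interaction and county. The interaction is tested at 5%, with acceptability as the primary provider outcome.
- Section 4.8 applies the same approach to PhenX outcomes in patients. It also uses linear regression of post-treatment credibility and perceived improvement on condition.
- For such comparisons 4.1 says: "Analyses comparing Adapted to Standard TranS-C will evaluate change in Generation 2 outcomes from pre-treatment to post-treatment and pre-treatment to 6FU".

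**Planning.** Section 3.8 treats Aim 2 as cluster randomised: 9 clusters, ICC 0.20, cluster-size coefficient of variation 0.75, detectable d = 0.70.

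**The concern.** A fixed county factor suits a comparison made within counties. It does not suit a comparison made between them, and two separate problems follow.

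First, condition is the sum of the dummies for the counties in one arm. In a single-time model the county factor therefore absorbs the whole condition effect. Software will drop condition and give no estimate, or drop one more county dummy and report a contrast between two reference counties under the label of condition.

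Secondly, in a repeated-measures model the county factor removes stable county differences but not differences between counties in change. The plan names no county-by-time variance, cluster-robust standard error or cluster-level degrees of freedom. The Aim 2 test then treats 60 providers as the independent units of a comparison that has nine randomised units. At stake is the error rate of the test on the primary provider outcome. Counties may well differ in change: section 3.1.2 lets trainers choose how they supervise, and section 3.2 says some centres mandate training while others leave it to interest.

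**Working it through.** **1. The plan's own figure.** From section 3.8: 60 providers, 9 clusters, ICC 0.20, CV 0.75, two-sided 5%, r = 0.83 to 0.85. Power is not stated; 80% is assumed.
- Mean cluster size m = 60/9 = 6.67.
- Design effect = 1 + [(1 + CV²)m − 1] × ICC = 1 + (1.5625 × 6.67 − 1) × 0.20 = 2.88.
- d = (1.96 + 0.842) × √[2 × 2.88 × (1 − r²)/30] = 0.69 at r = 0.83 and 0.65 at r = 0.85.

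This is close to the stated 0.70, so the planning calculation does allow for county clustering. With t quantiles on 9 − 2 = 7 df (2.365 + 0.896 = 3.261) the same formula gives 0.80 and 0.75.

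**2. Rank of the design matrices** (nine counties, each wholly in one condition).

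| Model | Columns | Rank | Condition main effect | Condition by time |
|---|---|---|---|---|
| 4.8 regression, one time | 1 + 1 + 8 = 10 | 9 | not estimable | none in model |
| 4.4 Aim 2, two times | 10 + 1 + 1 = 12 | 11 | not estimable | estimable |
| 4.8 PhenX, three times | 10 + 2 + 2 = 14 | 13 | not estimable | estimable |

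In the two- and three-time models the time terms and the within-arm county contrasts are also estimable. Adding fixed county-by-time terms to Aim 2 is no repair: the rank stays at 18 with or without condition by time, so the tested effect is aliased as well.

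**3. Error term in Aim 2.** With complete data the planned interaction equals the difference in mean provider change, tested against between-provider variation. A mixed-model fit and a t-test of change gave the same standard error (0.2405). If ρ is the county share of the variance in change, the true variance is larger by 1 + 9.42ρ, and the approximate type I error is 2[1 − Φ(1.96/√(1 + 9.42ρ))]. Simulation used nine unequal counties and an assumed 5:4 split.

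| ρ | 0 | 0.02 | 0.05 | 0.10 | 0.20 |
|---|---|---|---|---|---|
| Inflation factor | 1.00 | 1.19 | 1.47 | 1.94 | 2.88 |
| Formula | 5.0% | 7.2% | 10.6% | 16.0% | 24.8% |
| Simulation, as planned | 5% | 7% | 10% | 13-15% | 23-24% |

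A t-test on county mean changes with 7 df stayed at about 4 to 5% throughout.

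**4. Patient-level comparisons** (CV 0.72, taken from the patient planning figures in 3.8).

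| ICC | 0 | 0.05 | 0.10 | 0.20 |
|---|---|---|---|---|
| 130 patients, continuous change | 5% | 16% | 25% | 36-37% |
| 65 patients, single-time level | 5% | 9-10% | 14-15% | 24-25% |

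The first row illustrates the PhenX models only. Those outcomes are frequencies, quantities and suicidality items with skip rules, not continuous change scores. The second row is for the 4.8 regression read without county, where the relevant ICC is that of the post-treatment level. The Table 2 note says the CEQ was not given at the UC-DT post-treatment assessment. If delayed patients give no CEQ, about 130/2 = 65 patients remain (1:1 patient allocation assumed). If they give it after their delayed treatment, the 130-patient row applies.

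**The case against.** The certain failure is narrow. Aliasing removes the tested effect only in an exploratory regression, and only if the general rule in 4.1 governs a sentence in 4.8 that does not itself mention county. The analyst would notice at once. In Aim 2 the tested effect is estimable, and if counties do not differ in change the planned test is valid. The plan also says that few clusters motivated the choice, that ICCs will be reported, and that effect sizes will be read beside p-values.

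Much of this stands. A reader might infer that no Adapted-versus-Standard effect can be estimated. The documents do not support that, because 4.4 tests the interaction. A reader might also infer that Aim 2 runs at about 23% because 3.8 assumes an ICC of 0.20. That ICC is a planning value taken from provider-level studies and need not apply to change, so the inflation can only be shown as a range.

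The rest does not answer the point. Section 4.1 says all statistical models and exempts none. If 4.8 is read without county, the effect is estimable but is tested with patient-level error, which is valid only if counties do not differ. Having few clusters is a reason for small-sample degrees of freedom, not for leaving county out of the error term. Reported ICCs and effect sizes leave the standard error unchanged. The sensitivity analyses in 4.6 vary completion, substituted assessments and timing, not the error term.

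**Conclusion.** The concern holds, and the wording should be changed before analysis. Two statements are structural and certain: under 4.1 the credibility and improvement regression has no estimable condition effect, and the Aim 2 test contains no county-by-time variance. The size of the error in Aim 2 is conditional: none at a change ICC of 0, about double the nominal rate at 0.05, and 23-24% at 0.20. These figures assume complete data, a 5:4 county split and cluster sizes as planned in 3.8.

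The PhenX models share the structure of Aim 2, but their percentages are illustrative. Section 4.5 does not say how county enters Aim 3; if the 4.1 rule applies, the condition-to-fit path has the same problem. Aim 1 and Exploratory Aim 3 are unaffected, because patients are randomised to immediate or delayed treatment within county. The stated d = 0.70 is not shown to be wrong in itself. It belongs to a test that allows for clustering, which is not the test in 4.4.

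**What to change.** **Section 4.1.** Limit the county fixed factor to comparisons randomised within county.

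**Sections 4.4 and 4.8.** For Adapted versus Standard, drop the factor and prespecify one of these:
- a t-test on county means (single-time outcomes) or county mean changes (repeated outcomes), with df equal to contributing counties minus 2, which is 7 if all nine contribute; or
- a REML mixed model with a random county effect, plus random county-by-time for repeated outcomes, on the same df, kept even if the county variance is estimated as zero. In simulation with 20% of second ratings missing, normal quantiles in place of 7 df gave 9.9% type I error at ICC 0.20, against 5.5% with 7 df.

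The patient covariates promised in 4.1 can stay in the mixed model, or be handled by averaging covariate-adjusted residuals by county.

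**Section 4.5.** State that the county fixed factor is not entered on the condition-to-fit path and that inference on that path allows for county randomisation. Neither option above specifies the full multilevel structural equation model.

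**Section 3.8.** Recompute the Aim 2 detectable effect for the chosen test, stating the power, how r is used and the ICC of change.

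**Costs.** No new data are needed. Power falls: at change ICC 0 and d = 0.53 (the prior effect cited in 3.8, read here as a difference in change) it drops from 91-94% as written to 67-82%, in an aim that 3.8 already calls slightly underpowered. The mixed model is conservative at low ICC (1.6% at ICC 0) and departs from the rule in 4.1 that "Models will be estimated with maximum likelihood estimation". County means lose providers with only one rating, contrary to the all-available-data rule, and lose direct covariate adjustment.
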